## 7.1 Specification of Safety Parameters

We will monitor for all adverse events during the study. The Data Safety and Monitoring Board (DSMB) will monitor and review adverse events, and toxicities and events that may be related to the intervention. This will include verification that, when indicated, these events have been reported to the appropriate agencies (e.g. IRB) and that such reports have been made in a timely manner. The DSMB (TBN) will consist of a biostatistician, medical physician, clinical trials researcher, and clinical psychologist. [name] will also review information on the completeness of data and the rate of patient accrual relative to the protocol timeliness.

## 7.2 Adverse Events and Serious Adverse Events

Definition - An adverse event (AE) is any untoward medical occurrence in a subject temporally associated with participation in the clinical study or with use of the experimental agent being studied. An adverse finding can include a sign, symptom, abnormal assessment (laboratory test value, vital signs, electrocardiogram finding, etc.) or any combination of these.

A Serious Adverse Event (SAE) is any adverse event that results in one or more of the following outcomes:

- Death
- A life-threatening event

- Inpatient hospitalization or prolongation of existing hospitalization
- A persistent or significant disability/incapacity
- A congenital anomaly or birth defect
- Important medical event based upon appropriate medical judgment

Research staff and mind-body therapists will document and report solicited AEs including physical or psychological discomfort related to anxiety, blood pressure changes, depression, lightheadedness/dizziness, muscle cramps, musculoskeletal injury, or respiration. Unsolicited events will be captured through observation by research staff. Research staff will document unsolicited events and report AEs according to data safety monitoring plan. Events will be documented in the RedCap data entry system including date and time of event which will avoid double capture.

Adverse Reporting: The Independent Monitoring Committee (IMC) will monitor and review adverse events, and toxicities and events that may be related to the intervention.

- a) Non-serious adverse events will be reviewed on a monthly basis by the IMC. The IMC will be notified of serious adverse events within 24 hours of occurrence and reviewed within 48 hours.
- b) Unexpected fatal or life-threatening AEs related to the intervention will be reported to the NCCIH Program Officer within 7 days. Other serious and unexpected AEs related to the intervention will be reported to the NCCIH Program Official within 15 days.
- c) Anticipated or unrelated SAEs will be handled in a less urgent manner but will be reported to the Independent Monitor(s), IRB, NCCIH, and other oversight organizations in accordance with their requirements. In the annual AE summary, the Independent Monitor(s) Report will state that they have reviewed all AE reports.

### **7.3 Reporting Procedures**

Adverse events will be documented by research staff in RedCap as shown in Appendix for adverse event documentation. Research staff will notify [name] of non-serious adverse events within 24 hours. [name] will present all non-serious adverse events to the IMC for monthly review. Research staff will notify [name] of serious adverse events immediately. [name] will notify the IMC within 24 hours of occurrence, who will review the event within 48 hours. If upon review the SAE is determined to be related to the intervention, [name] will report the occurrence to the NCCIH program officer in 7 days for unexpected fatal or life threatening AEs and 15 days for other serious and unexpected AEs. After being informed, [name] will verify the severity of all AEs. [name] will initially assess if the AE is related to the study interventions as definitely, probably, possibly or unrelated. The IMC will review and confirm the relatedness and severity of AEs. AEs reports will be distributed to the IMC electronically via email.

### **7.4 Follow-up for Adverse Events**

AEs will be monitored by the IMC and [name] for recurrences, resolution, and ongoing toxicities that may be related to the intervention. Documentation and reporting for follow-up AEs will occur according to reporting procedures described in Section 7.3. The duration for follow-up will be for the length of the study period while patients are enrolled in the study. If non-serious adverse events are related to the breathing practice, then the protocol will be modified to avoid adverse events. If the frequency of non-serious adverse events is higher than anticipated or alters the benefit risk ratio, the study investigators after conferring with IMC, will also modify the breathing protocol. Two or more specific adverse events among subjects will prompt modification of the breathing protocol.

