#### **6.2.5 Completion/Final Evaluation**

- At 12 weeks
  - Autonomic tone
  - Catecholamine Profile
  - Questionnaires: PROMIS Anxiety Scale, Anxiety Sensitivity Index-3 (ASI-3), Beck Anxiety Inventory, Body Vigilance Scale, Panic Disorder Severity Scale, and Perceived Stress Scale-10, PROMIS Depression scale and PANAS-X.
  - Current Medications
  - Concomitant Interventions

Participants who discontinue the study intervention early will require no specific evaluations.

The reason for discontinuation will be documented. If research participants no longer want to participate in the research study, we will terminate them from the study. Participants terminated from the study will undergo no further monitoring or follow-up once they have stopped the study intervention.

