## 8. INTERVENTION DISCONTINUATION

The intervention will be discontinued for a participant if: 1) the intervention is associated with an adverse effect for a specific subject i.e. subject does not tolerate the intervention, 2) the subject no longer is interested or willing to receive the intervention or participate in the study, or 3) the subject's healthcare provider no longer recommends that the patient receive the intervention for medical reasons. The IMC and the principal investigator will review cases upon occurrence for discontinuation of intervention.

This study will be stopped prior to its completion if: (1) the interventions are associated with adverse effects that call into question the safety of the intervention, or (2) difficulty in study recruitment or retention will significantly impact the ability to evaluate the study endpoints, or (3) any new information becomes available during the trial that necessitates stopping the trial; or (4) other situations occur that might warrant stopping the trial.

Participants will be followed with their permission if the study is discontinued. The duration of follow-up will be length of the proposed study. We will continue to document adverse events, medications, and vital signs during the follow-up period.

Temporary discontinuation of the treatment may occur if the participants are absent due to travel/vacation, illness including hospitalization, non-compliance, or difficulties with transportation to sessions. Treatment will continue upon return to regularly scheduled sessions. We will continue to document adverse events and medications during temporary discontinuation.

Subjects may withdraw from the study at any time. Investigators may end the participation of the subject if they no longer qualify, have a serious adverse event, or upon request of the DSMB. To withdraw from the study, subjects will notify [name]. At that time, patients will no longer take part in any interventions and no further research data will be collected.

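### No supplied clause requires the outcome of a serious adverse event that is still unresolved when one participant's participation permanently ends

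*Combined protocol and SAP*

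**What the plan says.** Section 7.4 gives the IMC and a named study role the task of monitoring adverse events "for recurrences, resolution, and ongoing toxicities that may be related to the intervention". It then sets the period: "The duration for follow-up will be for the length of the study period while patients are enrolled in the study".

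Section 8 makes a serious event a possible reason for ending participation: "Investigators may end the participation of the subject if they no longer qualify, have a serious adverse event, or upon request of the DSMB". It also says that each discontinuation is looked at: "The IMC and the principal investigator will review cases upon occurrence for discontinuation of intervention".

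Section 8 describes two situations in which adverse events go on being documented after the intervention stops. One is a stop of the whole study, when participants are followed with permission for the planned length of the study. The other is a temporary break: "Temporary discontinuation of the treatment may occur if the participants are absent due to travel/vacation, illness including hospitalization", with the assurance that "We will continue to document adverse events and medications during temporary discontinuation".

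Section 6.2.5 says: "Participants terminated from the study will undergo no further monitoring or follow-up once they have stopped the study intervention". The sentence directly before it is "If research participants no longer want to participate in the research study, we will terminate them from the study".

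**The concern.** The purpose stated in section 7.4 is to see whether events recur, resolve or persist. The period stated in the same paragraph is the time on study. For most events the two agree. They conflict for a person whose participation is permanently ended by a serious event that has not yet resolved: the reason to follow is strongest just as the authority to follow lapses.

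What is at stake is participant safety and the quality of the safety review. Section 7 names stroke, serious arrhythmia and myocardial infarction as possible related events, and their course can run well past an initial review. Under section 7.3 the IMC confirms relatedness and severity. Under section 9.4 it decides whether the intervention continues, is modified or is discontinued after a related serious event. An outcome that nobody is required to obtain weakens those judgements. The efficacy estimates do not depend on this.

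**Working it through.** No calculation applies. The plan gives no figure on this point and no event rate from which to build one. The check is to take one participant whose participation is permanently ended by a serious event that is still unresolved, and to ask of each relevant clause whether it requires the outcome to be obtained.

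1. **Section 7.4, adverse event follow-up.** The purpose includes resolution, but the duration is tied to enrolment. Once participation has ended, the duty as written stops.
2. **Section 8, investigator-ended participation.** It gives the power to end participation for a serious event and attaches no follow-up duty.
3. **Section 8, temporary discontinuation.** Adverse events are still documented, and illness with hospitalization is a listed reason. Inpatient hospitalization is also a criterion for a serious event in section 7.2, so a hospitalized participant who stays in the study is covered. A participant whose exit is permanent is not.
4. **Section 8, whole-study stop.** Follow-up with permission is planned, including adverse events, medications and vital signs. It is triggered by the study stopping, not by one person leaving. The same participant with the same event would be followed if the trial closed that day, but not if only their own participation ended.
5. **Section 8, review of discontinuations.** The IMC and the principal investigator review the case when it occurs. This is a decision step at one point in time.
6. **Sections 7.2 and 7.3, reporting.** The IMC is notified of a serious event within 24 hours and reviews it within 48 hours. The funder receives reports of related unexpected events within 7 days (fatal or life-threatening) or 15 days (other serious). Anticipated or unrelated serious events are reported as each oversight body requires. These clauses govern initial reporting, and none asks for a later outcome.
7. **Section 9.4, suspension.** A related serious event suspends enrolment, the intervention or both until a safety review. The review may call for further investigation, but the clause does not require outcome follow-up of the person affected.
8. **Section 6.2.5, termination.** Read broadly, this rules out any follow-up. Read in context, it concerns people who no longer wish to take part. It does not supply the missing duty on either reading.
9. **Screening weeks.** Sections 5.1 and 6.2.1 start breathing instruction in the two screening weeks under a separate consent. Section 6.2.2 dates enrolment in the trial from after screening, although it also speaks of enrolling people for secondary screening. Whether section 7.4 reaches an event that ends participation in those two weeks is therefore unclear.

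None of the nine requires the outcome. Items 3 and 4 come closest, and each is limited to a different situation.

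**The case against.** The strongest objection is that the safety plan is spread over several documents and only one is available. Section 7.2 has adverse events reported under the Data Safety Monitoring Plan, section 7.5 says the independent monitoring is detailed there, and section 7.3 points to an adverse event appendix. A follow-up rule could sit in any of these. That stands as a limit on certainty. It does not remove the point, because section 7.4 is not silent: it states a duration, and a different rule elsewhere would have to be reconciled with it.

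A second objection is that the protocol never says when enrolment ends, so someone who stops sessions after a serious event might still count as enrolled. For a person who stops only the intervention, that is a fair reading. It is hard to sustain for someone whose participation the investigators have ended, which is the situation section 8 describes.

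A third is that the group is narrow: a serious event, then a discretionary decision, then a permanent exit, then an event still unresolved, among 100 healthy adults doing a low-risk intervention. This also stands and limits the size. It does not justify leaving the rule as written, given how little a change costs.

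A reader might go further in three ways that the documents do not support.

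- **That section 6.2.5 forbids all follow-up of anyone removed for a serious event.** Its preceding sentence is about people who no longer want to take part. Likewise, the section 8 sentence ending data collection follows directly on withdrawal at the subject's own notice.
- **That serious events in general go unfollowed.** Events in people who stay in the study, including those on a temporary break, are covered.
- **That the loss can be measured as the weeks left to week 12.** That is calendar time, not lost safety information.

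**Conclusion.** The point holds for the protocol as supplied. Section 7.4 ties adverse event follow-up to enrolment, section 8 allows participation to end because of a serious event, and no supplied clause requires the outcome of an event still unresolved when one person's participation permanently ends.

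Its size cannot be put as a number. Section 7 expects serious events related to the breathing practices to be very rare, but gives no rate for those or for serious events of any cause. The number affected is likely to be small. There is no effect on the treatment estimates or on power.

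The conclusion assumes that ending participation ends enrolment for the purposes of section 7.4, and that no rule in the unsupplied documents overrides it. Confidence is moderate for that reason. The change should be made because it protects participants at little cost, not because the trial's validity depends on it.

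**What to change.** Add to section 7.4, with matching exceptions in sections 6.2.5 and 8:

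- A serious adverse event, or an intervention-related adverse event that led to stopping, which is unresolved when participation ends is followed, with the participant's permission, until it resolves or stabilises.
- This includes participation that ends during the two screening weeks.
- Follow-up does not stop at week 12. A week-12 limit would give an event in week 11 only one more week and would defeat the purpose.
- Any outcome that cannot be obtained is reported to the IMC as unknown.

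Other non-serious events stay under the present rule. If the Data Safety Monitoring Plan or the adverse event appendix already contains such a rule, cite it in section 7.4 and bring the duration sentence into line.

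The cost is one or two sentences in section 7.4 and an exception clause in each of the other two sections. Because section 6.2.1 ties changes in research procedures to consent form revision and IRB review, a line in the consent form is also needed; since screening is included, both consents should carry it. In practice it means a few extra contacts for a small number of people, any of whom may decline.

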## 7.5 Safety Monitoring

This Human Subjects research study will undergo independent monitoring from an IMC, which is described in detail in the Data Safety Monitoring Plan (DSMP) Monitoring Committee under the guidelines provided by NCCIH. The IMC will meet prior to enrollment of subjects into studies.

## 8. INTERVENTION DISCONTINUATION

The intervention will be discontinued for a participant if: 1) the intervention is associated with an adverse effect for a specific subject i.e. subject does not tolerate the intervention, 2) the subject no longer is interested or willing to receive the intervention or participate in the study, or 3) the subject's healthcare provider no longer recommends that the patient receive the intervention for medical reasons. The IMC and the principal investigator will review cases upon occurrence for discontinuation of intervention.

This study will be stopped prior to its completion if: (1) the interventions are associated with adverse effects that call into question the safety of the intervention, or (2) difficulty in study recruitment or retention will significantly impact the ability to evaluate the study endpoints, or (3) any new information becomes available during the trial that necessitates stopping the trial; or (4) other situations occur that might warrant stopping the trial.

Participants will be followed with their permission if the study is discontinued. The duration of follow-up will be length of the proposed study. We will continue to document adverse events, medications, and vital signs during the follow-up period.

Temporary discontinuation of the treatment may occur if the participants are absent due to travel/vacation, illness including hospitalization, non-compliance, or difficulties with transportation to sessions. Treatment will continue upon return to regularly scheduled sessions. We will continue to document adverse events and medications during temporary discontinuation.

Subjects may withdraw from the study at any time. Investigators may end the participation of the subject if they no longer qualify, have a serious adverse event, or upon request of the DSMB. To withdraw from the study, subjects will notify [name]. At that time, patients will no longer take part in any interventions and no further research data will be collected.

## 9. STATISTICAL CONSIDERATIONS

### 9.1 General Design Issues

All analyses will be performed as intention-to-treat. Our intent-to-treat population will include all participants who are randomized with baseline assessment and at least one post-randomization assessment.

**Specific Aim 1:** Compare 12 weeks of slow breathing exhale>inhale vs. exhale=inhale on changes in physiological stress (**primary outcome: heart rate variability**, secondary outcomes: baroreflex sensitivity, catecholamines).

**Primary hypotheses:** *We hypothesize that participants with exhale>inhale vs. exhale=inhale will have higher increases in parasympathetic tone as measured by the HFHRV.*

**Secondary hypotheses:**

3. *We hypothesize that participants with exhale>inhale vs. exhale=inhale will have higher increases in parasympathetic tone as measured by baroreflex sensitivity alphaindex.*
4. *We hypothesize that baseline parasympathetic tone will modify response to breathing interventions. Specifically, we hypothesize that participants with lower parasympathetic tone at baseline will have the greater increases in parasympathetic tone as measured by HF HRV and BRS alpha index.*

**Specific Aim 2:** Compare 12 weeks of slow breathing exhale>inhale vs. exhale=inhale on changes in psychological stress (**primary outcome- anxiety**, secondary outcomes: perceived stress, arousal, and affect).

**Primary hypotheses:** *We hypothesize that participants with exhale>inhale vs. exhale=inhale will have further decreases in psychological stress as measured by the PROMIS Anxiety scale.*

**Secondary hypotheses:**

*We hypothesize that participants with exhale>inhale vs. exhale=inhale will have further decreases negative affect as measured by PROMIS Depression and PANAS-X and stress as measured by Perceived Stress Scale, Anxiety Sensitivity Index-3, Beck Anxiety Inventory, Body Vigilance Scale, and the Panic Disorder Severity Scale*

*We hypothesize that baseline psychological stress will modify response to breathing interventions. Specifically, we hypothesize that participants with higher anxiety at baseline will have the further decreases in anxiety as measured by the PROMIS anxiety instrument.*

**Exploratory research questions:** We consider arousal as an exploratory measure in this proposal. In our pilot, exhale>inhale had improvements in daytime arousal vs. exhale=inhale as measured by the Epworth Sleepiness Scale. For the present proposal, we will examine differences in arousal from

baseline, 6, to 12 weeks as measured by the Epworth Sleepiness Scale. We will also explore the relationship between baseline sleep disturbance as measured by the PROMIS Sleep Disturbance scale and changes in arousal. We will also explore if there are any sustained changes at 26 week in psychological measures and if participants continue to breathe after the intervention.

**Specific Aim 3:** Compute the correlation between physiological and psychological changes (e.g. changes in heart rate variability correlated with changes in anxiety).

**Main hypotheses:** *We hypothesize that changes in physiological and psychological measures will be moderately correlated.*

**Analyses in preparation for second phase of research project (R33):** A After reaching 100% enrollment and baseline data collection, we will perform analyses of baseline data to identify a targeted population for the second phase. The purpose of these analyses is to examine the distribution of selected physiological and psychological stress measures in the general population. We will compare baseline data collected with other collected data or published studies. To identify a study population for R33 phase, we will choose stress thresholds (lower limit) based on the median of the general population or the lower quartile of previously-studied known high-stress population, whichever is higher.

Alternative: We will investigate the effect of baseline physiological and psychological stress level on the intervention-induced stress change using smoothing splines with adequate knots, and identify a starting point of baseline stress level that is associated with desirably large change. Subjects with baseline stress level higher than this point will be enrolled for R33 phase study.

**Anticipated Results:** We expect that both exhale=inhale and exhale>inhale slow breathing will improve physiological and psychological relaxation, and that extending the length of exhale will show greater benefits.

Compared to exhale=inhale, exhale>inhale slow breathing will have greater increase in HF HRV and baroreflex sensitivity (Aim 1). Exhale>inhale slow breathing will also have further decrease in the PROMIS Anxiety instrument (Aim 2). In addition, we expect that the changes in HF HRV will correlate with changes in Perceived Stress Scale in a moderate way (Aim 3).

